	7.6.1 Primary Analyses	
	7.6.2 Secondary Analyses	

8.0	HUMAN SUBJECTS CONSIDERATIONS	17
8.1	Ethical Review	17
8.2	Informed Consent	17
8.3	Risks	17
8.4	Benefits	18
8.5	Incentives	18
8.6	Confidentiality	18
8.7	Study Discontinuation	19
9.0	LABORATORY SPECIMENS AND BIOHAZARD CONTAINMENT	19
9.1	Local Laboratory Specimens	19
9.2	Reference Laboratory Specimens	19
9.3	Specimen Storage and Possible Future Research Testing	19
	REFERENCES	

LIST OF ABBREVIATIONS AND ACRONYMS

AE Adverse Event

CKD Chronic kidney disease EAE Expedited Adverse Event

EC ethics committee

FDA (United States) Food and Drug Administration

GCP Good Clinical Practices
IRB Institutional Review Board

LDMS Laboratory Data Management System

LL Local Laboratory

MRS/OS ³¹P Magnetic resonance spectroscopy and optical spectroscopy

NIDDK United States) National Institute of Diabetes and Digestive and Kidney

NIH (United States) National Institutes of Health

PAT Pulse amplitude tonometry ROC Regulatory Operations Center

SAE Serious Adverse Event

SDMC Statistical and Data Management Center

SUSAR Suspected Unexpected Serious Adverse Reaction

SOP Standard Operating Procedures SSP Study Specific Procedures

TCA Tricarboxylic acid (Krebs) cycle

SCHEMA

Purpose: Study the impact of oral glutamine supplementation on mitochondrial

function and endothelial cell function measured by ³¹P MRS/OS among

persons with moderate-severe CKD.

Design: Randomized, placebo controlled cross-over trial

Study Population: Moderate-severe CKD with eGFR by CKD (EPI equation) $\leq 60 \text{ml/min}/1.73 \text{m}^2$

Study Size: 20

Treatment Regimen: - Oral glutamine 0.4gm/kg/day

- Placebo

Study Duration: 1 year

Primary Objectives:

• To test if glutamine supplementation improves mitochondrial function and vascular function as measured by ³¹P MRS/OS.

Secondary Objectives:

[figure not shown]
- To test the effects of oral glutamine supplementation on metabolic response profile.
- To test if glutamine supplementation reduces inflammatory and oxidative stress biomarkers.
- To test if glutamine improves objective isometric muscle fatigue.
- To test if glutamine supplementation reduces proteinuria (albuminuria).
- To test if glutamine supplementation reduces 24 hour urine urea nitrogen.

Study Sites:

University of Washington:

- University of Washington Medical Center Translational Center for Metabolic Imaging
- Kidney Research Institute:
 - o KRI at Harborview Medical Center

1.0 INTRODUCTION

1.1 Background and Prior Research

Chronic kidney disease is associated with vascular dysfunction leading to substantial cardiovascular and cerebrovascular disease burden. A major mechanism of vascular dysfunction is thought to be endothelial cell dysfunction due to the accumulation of homocysteine, asymmetric di- and mono-methylarginines (ADMA), reactive oxygen species, and/or guanidine-compounds. Current standard of care for treating vascular disease in patients with CKD focuses on addressing of hypertension and proteinuria, both of which are detected late in the disease. The observation that endothelial cell dysfunction (ECD) develops at earlier, pre-uremic stages of CKD highlights the critical need for investigations into earlier preclinical mechanisms contributing to ECD.

Defects in endothelial nitric oxide synthase (eNOS) and/or deficiency of bioavailable nitric oxide are the hallmarks of endothelial cell dysfunction leading to vascular disease and defective angiogenesis. Accumulation of toxins found in renal disease may impact endothelial cell nitric oxide bioavailability and eNOS function. Indeed, exposure of endothelial cells to asymmetric dimethylarginines (ADMA) has been shown to result in the redistribution of eNOS from the plasma membrane to the mitochondrion as well as result in uncoupling of eNOS with enhanced generation of reactive oxygen species. Furthermore substantial evidence indicates nitric oxide bioavailability is linked to mitochondrial biogenesis. Recent observations of a proteomic signature in early ECD modeled by using chronic L-NMMA treatment akin to elevation on ADMA suggest underlying mitochondrial dysfunction. Under these conditions early ECD is characterized by reductions in aconitase-2 and ECHS-1 (key enzymes in the mitochondrial TCA cycle and fatty acid beta oxidation pathways). Reactive oxygen species have been shown to play a central role in inactivation of aconitase. These findings may suggest that inhibition of the Krebs cycle and mitochondrial bioenergetics may augur the development of ECD. Deficiency in these enzymes and reduction in mitochondrial mass may result in a metabolic block of normal mitochondrial oxidative phosphorylation.

Glutamine is a potent anaplerotic (capable of replenishing intermediates of the Kreb's cycle) and a potential therapeutic agent bypassing the metabolic block associated with reduced TCA cycle activity and impaired mitochondrial function (figure 1). It is also the substrate for glutamate important for antioxidant glutathione synthesis. It has been demonstrated to confer metabolic benefits in other populations, but the data on its effect in patients with chronic kidney disease are unknown. Here we assemble a multidisciplinary team of investigators with expertise in physiology, biophysics, and

[figure not shown]

Figure 1. Supplementation with glutamine: its conversion to alpha-ketoglutarate bypasses the enzymatic block in ECD and reinforces the truncated Krebs cycle.

nephrology to investigate the impact of glutamine on mitochondrial energetics and vascular function.

We propose a phase II randomized, controlled cross-over trial of glutamine supplementation on mitochondrial energetic and endothelial function measured by non-invasive ³¹P magnetic resonance spectroscopy coupled with optical spectroscopy (MRS/OS) and pulse amplitude tonometry among persons with moderate-severe chronic kidney disease.

1.2 Rationale

Chronic kidney disease is associated with endothelial cell dysfunction and muscle wasting contributing to the heightened risk of cardiovascular morbidity and mortality and functional limitation. Accumulation of toxins in renal disease may adversely impact endothelial cell nitric oxide bioavailability and endothelial Nitric Oxide Synthase (eNOS) function consequently heightening oxidative stress and suppressing mitochondrial biogenesis. To date no studies have investigated potential therapies for endothelial and muscle dysfunction in renal disease target mitochondrial metabolic and energetic processes.

Animal studies of uremia underscore mitochondrial dysfunction as a potential precursor for endothelial dysfunction. In particular, uremia has been linked to a proteomic signature indicative of metabolic blockage of TCA cycle activity and fatty acid beta-oxidation. Both of these processes are localized to the mitochondria and may suggest that decreased mitochondrial mass or function may augur endothelial dysfunction in renal disease.

Glutamine, an anaplerotic agent and precursor to the antioxidant glutathione, is a potential therapeutic agent bypassing the metabolic block associated with reduced TCA cycle and improving antioxidant reserve. A recent dose-finding study and randomized controlled trial of glutamine in patients with critical illness demonstrated that an IV dose of 0.35g/kg/day by ideal body weight was associated with an increased muscle mitochondrial mass¹ and well tolerated without any serious clinical or biochemical adverse events compared to placebo.²

The primary goal of proposed investigation is to study the impact of oral glutamine supplementation on muscle mitochondrial and endothelial cell function measured mitochondrial energetics and vascular function using ³¹P MRS/OS among persons with moderate-severe CKD. The secondary objective is to describe the impact of oral glutamine supplementation on mitochondrial metabolic profile as well as inflammatory and oxidative stress biomarkers among persons with chronic kidney disease.

2.0 STUDY OBJECTIVES AND DESIGN

2.1 Primary Objectives

The primary objectives of this study are to:

• To test if glutamine supplementation improves mitochondrial function and vascular function as measured by ³¹P MRS/OS.

2.2 Secondary Objectives

The secondary objectives of this study are to:

- To test the effects of oral glutamine supplementation on metabolic response profile.
- To test if glutamine supplementation reduces inflammatory, oxidative stress biomarkers and redox proteome
- To test if glutamine improves objective isometric muscle fatigue.
- To test if glutamine supplementation reduces proteinuria (albuminuria).
- To test if glutamine reduces 24 hour urine urea nitrogen.

2.3 Study Design

Overview of study design

This is a placebo-controlled, double-blind crossover trial. There are 2 phases 14 days each separated by a 3-week washout period

A brief screening visit will assess eligibility criteria, and will include informed consent. Qualified participants will be stratified by diabetes status and randomly assigned (1:1) to 14 days of placebo followed by 14 days weeks of oral L-glutamine, or 14 days of oral L-glutamine followed by 14 days of placebo, each separated by a 3-week wash-out period.

Qualified participants will participate in 3 study visits, plus a screening visit. Study outcomes will be assessed at each of these 3 visits.

Subjects will receive 0.4 g/kg/day of L-glutamine in three divided daily doses. This dose was chosen based on a review of studies in the literature evaluating biological activity of glutamine on immune function and modulation of muscle turnover. Placebo will consist of identical appearing maltodextrin powder.

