3.2 Exclusion Criteria

Criteria included in MEND:

- Pregnant
- Kidney transplantation
- Weight >400 lbs
- HIV infection
- End stage liver disease with cirrhosis
- Have physical immobility (defined by wheelchair use, oxygen-dependent COPD, shortness of breath after <100 steps)
- Have implants incompatible with MRI
- Institutionalization, or inability to consent
- Use medications interfering with muscle or mitochondrial function, including steroids, anti-psychotic, antivirals, muscle relaxants, oral calcineurin inhibitors, and anti-epileptic drugs
- Active malignancy
- Pacemaker
- Current participation in another interventional trial
- Non-English speaking

Additional Criteria:

- On chronic dialysis
- Expectation to start dialysis within 6 months or dialysis access in place.
- Insulin dependent diabetes
- Exercise limiting cardiopulmonary disease (e.g. angina, severe heart valve disease, severe COPD, coronary ischemia)
- Use of anticoagulation (i.e. warfarin)
- Baseline systolic blood pressure >170 or diastolic blood pressure >100
- Inflammatory conditions (e.g. autoimmune disease, HIV)
- Cirrhosis, active/chronic hepatitis
- Weight >300 lbs
- Personal history or family history of deep vein thrombosis, pulmonary embolism
- Patients hospitalized within the past 60 days for any reason.

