7.3 Accrual, Follow-up, and Sample Size

The overall sample size for this project is 20. We anticipate recruiting 1-2 participants weekly for total study duration of 2 years.

Sample size was calculated based on values obtained from an estimated within individual coefficient of variation in values of ATP/O₂ ratio from MRS/OS of approximately 15% and values of test-retest reliability of pulse amplitude tonometry measures of vascular endothelial function from a recent published study. A total of 20 patients will enter this two-treatment crossover study. With this sample size, the probability is over 90% that we will detect a meaningful treatment difference of 20% for ATP/O2 ratio at a one-sided 0.05 significance level (Table 2). This is based on the assumption that the within-patient standard deviation of the response variable is 0.375 with a mean predicted ATP/O2 ratio of 2.5. Sample size was calculated using the following sample size calculator: http://hedwig.mgh.harvard.edu/sample_size/js/js_crossover_quant.html

	ATP/O ₂ ratio	
	Power	
Minimal detectable difference	80%	90%
20%	6	7
25%	4	5
33%	4	4
40%	3	4

Table 2. Samples size required to detect treatment effects for ATP/O2 ratio from MRS/OS and reactive hyperemia index (RHI) from PAT in crossover design.

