7.4 Random Assignment / Study Arm Assignment

Investigational drug services will be responsible for randomization of participants into the two treatment groups.

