7.6 Data Analysis

7.6.1 Primary Analyses

The major assumption in the cross-over trial is that there is no carryover effect of first period into the second period. The assumption is that a 3-week washout will be sufficient

to eliminate any potential carryover effect due to glutamine. The statistical model we assumed for continuous data from the 2×2 crossover trial:

Design	Period 1	Period 2
Sequence Placebo-Gln	A	В
Sequence Gln-Placebo	В	A

From this design we construct these differences for every patient and compare the two sequences with respect to these differences using a two-sample paired t test. Thus, we are testing:

$$H_0: \mu_{AB} - \mu_{BA} = 0$$

Where:
$$\mu_{AB} - \mu_{BA} = 2(\mu_A - \mu_B)$$

So testing
$$H_0: \mu_{AB} - \mu_{BA} = 0$$
, is equivalent to testing:

$$H_0: \mu_A - \mu_B = 0$$

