7.6.2 Secondary Analyses

We will test for difference in each marker of metabolic response profile, oxidative stress, and albuminuria in a similar fashion as above. Similar to above, we will use a two-sample paired t-test testing the difference in means comparing treatment to placebo.

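### Randomisation is stratified by diabetes, but the analysis has no diabetes term, so any diabetes difference in period effect stays in the error and costs precision

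*Combined protocol and SAP*

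**What the plan says.** Section 2.3 (Study Design): "Qualified participants will be stratified by diabetes status and randomly assigned (1:1" to placebo then glutamine, or glutamine then placebo.

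Section 7.4 (Random Assignment) does not repeat the stratification or describe blocks. It says only that "Investigational drug services will be responsible for randomization of participants into the two treatment groups".

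Section 7.6.1 forms a difference for each patient and will "compare the two sequences with respect to these differences using a two-sample paired t test". Section 7.6.2 carries the same approach to the secondary markers: "we will use a two-sample paired t-test testing the difference in means comparing treatment to placebo". Neither has a diabetes term, a stratified test or a stratum-weighted estimate, and no other section brings diabetes into an analysis.

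Section 3.2 excludes "Insulin dependent diabetes", so the diabetes stratum holds only patients whose diabetes is not insulin dependent. No quota or expected share is given for it.

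**The concern.** A factor used to balance the sequences would normally also appear in the analysis. In a crossover the usual reason, removing between-patient variation, mostly falls away, because each patient is his or her own control. A diabetic patient whose ATP/O2 ratio is lower in both periods contributes nothing extra to the period difference.

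What survives differencing is a change over time that differs between strata. If diabetic patients drift between day 15 and day 53 and the others do not, or drift differently, the period differences have two different centres within each sequence. The t test treats that spread as random error. Stratification has balanced the sequences on this source of variation, but the test takes no credit for it. At stake is the width of the confidence intervals in a 20-patient trial, for four primary measures and a long list of secondary markers.

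**Working it through.** **Inputs from section 7.3.** N = 20, taken as 10 per sequence (section 4.3 aims for 10 completers per arm). Test "at a one-sided 0.05 significance level". Assumption: "the within-patient standard deviation of the response variable is 0.375 with a mean predicted ATP/O2 ratio of 2.5". Target effect: 20% of 2.5 = 0.50 units.

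**The plan's own figure.** The claim is that "the probability is over 90% that we will detect a meaningful treatment difference of 20% for ATP/O2 ratio". I used the noncentral t distribution for the mean within-patient difference, with N − 1 df.

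| Reading of 0.375 | SD of difference | Table 2, 20% row (80% / 90% power) | Power at N = 20 |
|---|---|---|---|
| SD of the difference | 0.375 | 6 / 7, as printed | >0.999 |
| Within-patient SD | 0.375 × √2 = 0.530 | 9 / 12 | 0.992 |

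The first reading reproduces all eight cells of Table 2; the second is what the text says. Power exceeds 90% on both, so I carry both forward.

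**Assumed inputs, not in the documents.** Share with diabetes p = 0.5. D, the stratum difference in period effect, = 0.25 or 0.50 ATP/O2 units. Sequences balanced within strata.

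**Variance left in the error term.** Extra variance = p(1 − p)D².
- D = 0.25: 0.25 × 0.0625 = 0.0156.
- D = 0.50: 0.25 × 0.25 = 0.0625.

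| Variance of a period difference | D = 0.25 | D = 0.50 |
|---|---|---|
| 2 × 0.375² = 0.281 | +6% (SE +3%) | +22% (SE +11%) |
| 0.375² = 0.141 | +11% (SE +5%) | +44% (SE +20%) |

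At p = 0.3, p(1 − p) is 0.21 instead of 0.25. The first row becomes +5% and +19%, the second +9% and +37%.

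**Effect on the standard error.** The treatment effect is half the difference between sequence means, so SE = ½ × √[v × (1/10 + 1/10)]. With v = 0.281 this is 0.119. With v = 0.281 + 0.0625 = 0.344 it is 0.131. Simulation at D = 0.50 agrees: the unstratified SE averages 0.132 against a true sampling SD of 0.117 to 0.120, whether the diabetic share is fixed or random. With a diabetes main effect in the model the SE is about 0.119.

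**Operating characteristics** (simulation, N = 20, p = 0.5, one-sided 0.05):

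| SD of difference | D | Type I error: no stratum / with stratum | Power: no stratum / with stratum |
|---|---|---|---|
| 0.530 | 0.25 | 0.044 / 0.048 | 0.990 / 0.991 |
| 0.530 | 0.50 | 0.034 / 0.050 | 0.986 / 0.992 |
| 0.375 | 0.25 | 0.041 / 0.049 | >0.999 / >0.999 |
| 0.375 | 0.50 | 0.024 / 0.050 | >0.999 / >0.999 |

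The phrase "we will use a two-sample paired t-test testing the difference in means comparing treatment to placebo" could also mean an ordinary paired t test. That test is conservative to the same degree (type I error 0.034 at SD 0.530, D = 0.50).

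**Cost of the extra term.** Residual df fall from 18 to 17, and the one-sided 5% critical value rises from 1.734 to 1.740, about 0.3%.

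**The case against.** The strongest reply is that nothing the sponsor will decide depends on this. ATP/O2 has a large reserve of power, the error is on the safe side, and no figure in the documents suggests that diabetes alters the period effect. All of that stands for ATP/O2, and it is why the point is minor. It does not carry over to ATPmax, O2max, the vascular delay or the secondary markers, for which section 7.3 states neither an SD nor a power.

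A reader might infer something stronger: that a diabetes difference in the *treatment* effect also makes the planned standard error too wide, so the primary analysis should include a treatment-by-diabetes term. The documents do not support that. They fix no diabetes share, so the share in the sample is random and the average treatment effect truly varies with it. For a 0.5-unit difference in treatment effect (SD of difference 0.530), simulation gives an unstratified SE of 0.132 against a true 0.130, which is correct. The interaction model gives 0.119 against 0.130, which is too small, and a one-sided type I error of 0.0625. Only if the share is regarded as fixed is the unstratified SE too wide (0.132 against 0.119).

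Nor should a reader infer that leaving out the stratum biases the estimate or inflates the type I error.

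**Conclusion.** The point holds as a minor matter of precision. The plan stratifies on diabetes and then does not use it, so a diabetes difference in period effect would stay in the error term. Under the assumed inputs (half the patients diabetic, D of 0.25 to 0.50), residual variance is 6% to 22% or 11% to 44% too large, depending on what 0.375 measures. The test becomes conservative, and the loss of ATP/O2 power is under one percentage point.

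Two conditions apply. If the strata share the same period effect, nothing is lost. And the statement that the SE is too wide assumes the sequences end up balanced within strata. Section 7.4 gives no scheme that ensures this, and section 4.3 allows for drop-out. Without that balance the extra variance is real noise in the unadjusted estimate. The stratum term removes it in either case.

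**What to change.** In 7.6.1 and 7.6.2, replace the t test with a linear model of each patient's period 1 minus period 2 difference on sequence and diabetes stratum. Report half the sequence contrast, signed as glutamine minus placebo, as the primary treatment effect. With complete data, a mixed model with treatment, period, diabetes and diabetes-by-period terms is equivalent. Naming the model also settles what a two-sample paired test was meant to be.

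Keep any sequence-by-diabetes (that is, treatment-by-diabetes) term as a supportive analysis only. Weight the strata by observed size, and state that its standard error applies to the effect at the sample's own diabetes mix. Equal weights would be costly with a small stratum: with 4 diabetic patients of 20, the variance is ¼(1/4 + 1/16) = 0.078 against 1/20 = 0.050, a rise of 56%.

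In 7.4, restate the stratification from 2.3 and say how balance within strata is achieved.

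The cost is SAP wording and one degree of freedom. Diabetes status is already needed for randomisation, so no new data are required.

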3.0 STUDY POPULATION

Study participants will be selected from patients with moderate-severe CKD not treated with dialysis from the Muscle Mitochondrial Energetics and Dysfunction (MEND) study, a cross-sectional clinic-based study of CKD. MEND has recruited CKD and end stage renal disease (ESRD) patients from Nephrology clinics at Harborview Medical Center, University of Washington Medical Center, and the Northwest Kidney Centers. MEND includes a diverse population, representing the greater population of those with kidney disease. Exclusion criteria for MEND include kidney transplantation, non-English speaking, unable to provide informed consent, or dementia.

Participants will be selected for this study from MEND according to the criteria in Section 3.1 and 3.2. They will be recruited, screened, and enrolled as described in Section 3.3 [and assigned to a study treatment/intervention group as described in Section

7.4]. Issues related to participant retention and withdrawal from the study are described in Sections 3.5 and 3.6, respectively.

3.1 Inclusion Criteria

Criteria included in MEND:

Additional Criteria:

- Adults between 20 and 79 years of age
- Diagnosis of moderate-severe CKD, defined in this study as an estimated glomerular filtration rate (eGFR) of ≤60ml/min/1.73m² using the Chronic Kidney Disease Epidemiology Collaboration equation

3.2 Exclusion Criteria

Criteria included in MEND:

- Pregnant
- Kidney transplantation
- Weight >400 lbs
- HIV infection
- End stage liver disease with cirrhosis
- Have physical immobility (defined by wheelchair use, oxygen-dependent COPD, shortness of breath after <100 steps)
- Have implants incompatible with MRI
- Institutionalization, or inability to consent
- Use medications interfering with muscle or mitochondrial function, including steroids, anti-psychotic, antivirals, muscle relaxants, oral calcineurin inhibitors, and anti-epileptic drugs
- Active malignancy
- Pacemaker
- Current participation in another interventional trial
- Non-English speaking

Additional Criteria:

- On chronic dialysis
- Expectation to start dialysis within 6 months or dialysis access in place.
- Insulin dependent diabetes
- Exercise limiting cardiopulmonary disease (e.g. angina, severe heart valve disease, severe COPD, coronary ischemia)
- Use of anticoagulation (i.e. warfarin)
- Baseline systolic blood pressure >170 or diastolic blood pressure >100
- Inflammatory conditions (e.g. autoimmune disease, HIV)
- Cirrhosis, active/chronic hepatitis
- Weight >300 lbs
- Personal history or family history of deep vein thrombosis, pulmonary embolism
- Patients hospitalized within the past 60 days for any reason.

